### 5.3 Safety Population

The safety set will consist of all subjects who sign informed consent and are thus enrolled. The Safety population will be analyzed based on actual treatment received.

## 6. STUDY DAY AND VISIT WINDOW DEFINITION

### 6.1 Study Day

For each subject, the day of randomization will be considered study day 0. The day of the week 12 assessment will be considered study day 0 in the open label period. Each assessment will be assigned a study day. The calculation for study day is dependent on whether the actual date of assessment is before or after the date of randomization and is calculated as follows:

Run in period:

Study day = (date of enrollment – randomization date) (results in negative numbers)

Randomized period (Visits up to but not including the week 12 assessment):

Study day = (date of assessment – randomization date)

Open label period (Starting with week 12 assessment):

Study day (with reference to randomization date) = (date of assessment – randomization date - 1)

Study day (in open label period) = (Date of assessment – date of entry into OL period)

If the full date of the assessment is not known, then no study day will be assigned.

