## 7.4 Efficacy

### 7.4.1 Primary Endpoint

The primary endpoint is the change from run-in to the last four weeks (Month 3) of the randomized period in the number of migraine days.

The diary data will collect for each day an indicator (1=Yes, 0=No, or missing) of whether the subject experienced a migraine. One 24 hour period per migraine will be designated as a migraine day.

The visit level value for a given subject is then the sum of the daily diary day indicators of whether the subject experienced a migraine which gives the number of days with a migraine. Calculations are as follows:

$$\text{Run-in Value} = \sum_{i=-z-28}^{-z} \text{Day } i, \text{ where Day } i = 1 \text{ (had a migraine)}$$

where  $z$  represents the subject's last day with diary data during the run-in period.

In the event that a subject does not 28 diary days in the run-in period the following rules will be used to calculate the run-in value:

1. If the number of diary days in the run-in period is less than 21, the run-in value will not be calculated, and will be considered missing.
2. If number of diary days in the run-in period is greater than or equal to 21, but less than 28, the run-in value would be calculated as:

$$\text{Run-in Value} = \sum_{i=-z-x}^{-z} \text{Day } i, \text{ where Day } i = 1 \text{ (had a migraine)}$$

where  $z$  represents the subject's last day with diary data during the run-in period, and  $x$  is the number of days with diary data during the run-in period.

To ensure consistency of the run-in value for all subjects, the value will be adjusted to reflect an estimated number of days with migraine per 28 day interval. For example, if a subject records data for  $x$  days out of 28 days and have  $y$  days with migraine, then the adjusted number of days with migraine in 28 days is  $(28/x)*y$ , with a maximum value of 28.

$$\text{Month 3 Value} = \sum_{i=57}^{84} \text{Day } i, \text{ where Day } i = 1 \text{ (had a migraine)}$$

In the event that a subject does not have at least 84 study days in the DB period the following rules will be used to calculate the Month 3 value:

3. If the number of study days in the DB period is less than 70, the month 3 value will not be calculated, but rather imputed to the run-in value (and thus resulting in a  $\text{Change}_{\text{Run-in}}=0$ , implying no change between periods).

Month 3 Value =Run-in Value

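### SAP section 6.1 breaks the day count at week 12, so the Month 3 window and the 84-day requirement do not line up with the blinded period

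*SAP*

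**What the plan says.** Section 6.1 fixes the origin: "the day of randomization will be considered study day 0". It then gives two rules for counting from randomization.

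- Before week 12, under "Randomized period (Visits up to but not including the week 12 assessment", the rule is "Study day = (date of assessment – randomization date".
- From week 12, under "Open label period (Starting with week 12 assessment", the rule is "Study day (with reference to randomization date) = (date of assessment – randomization date - 1".

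The same section also states: "The day of the week 12 assessment will be considered study day 0 in the open label period". The V6 date is therefore outside the randomized period and is the zero point of the next one.

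Three other places depend on this numbering.

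- Section 6.3 starts Month 1 at Day 1 and makes Month 3 Days 57-84.
- Section 7.4.1 sums migraine days over Days 57-84. Special rules apply "In the event that a subject does not have at least 84 study days in the DB period". For 70 to 83 study days, rule 4 sums from Day 1 to the last diary day and rescales to 28 days.
- Table 2 labels the randomization visit (V2, week 0) Day 1 and V6 (week 12) Day 84, with a window of 5 days either side.

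The run-in line of section 6.1 reads "Study day = (date of enrollment – randomization date", which uses the enrollment date where the other lines use the assessment date.

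**The concern.** The two formulas differ by one day and meet at V6, so the numbering cannot run cleanly across the end of the blinded period. The primary endpoint uses these numbers twice: to choose the diary days that are summed, and to decide whether a subject gets the full calculation or a partial-data rule. An error of one day can therefore let an open-label day into a blinded endpoint, or move a subject who attended on schedule to a different calculation. Under section 7.4.2, headache days and acute-medication days are derived in the same way, and responder status is computed from the same migraine-day value, so these endpoints inherit whatever is decided here.

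**Working it through.** **Inputs.** Let d be calendar days since randomization. Section 6.1 gives study day = d before V6 and d - 1 from V6 on. Section 6.3 gives Month 3 = Days 57-84. Section 7.4.1 gives the 84-day requirement. Table 2 puts V6 at week 12, Day 84.

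**Does the plan's own Day 84 come back?** Put V6 at randomization+84, which is 12 x 7 days from a Day 0 origin.

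| Date | Formula | Study day |
|---|---|---|
| randomization+83 (last day before V6) | d | 83 |
| randomization+84 (V6) | d - 1 | 83 |
| randomization+85 (first day after V6) | d - 1 | 84 |

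It does not. V6 is Day 83, the number 83 is used twice, and Day 84 is an open-label date.

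**Effect on the Month 3 window.** If diary days are numbered by these formulas, Days 57-84 run from randomization+57 to randomization+85. That is 85 - 57 + 1 = 29 dates: 27 before V6, the V6 date, and one day after it. With d used throughout, Days 57-84 are randomization+57 to randomization+84, which is 28 dates ending on V6. The excess is one day: 1/28 = 3.6%.

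**Effect on the 84-day requirement.** With the V6 date in the open-label period, the last blinded date is randomization+83.

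- Counting Days 1-83, as section 6.3 implies by starting Month 1 at Day 1: 83 study days. This is below 84, so rule 4 applies.
- Counting Days 0-83: 84 study days. The requirement is met.
- Counting Days 1-84 with V6 treated as blinded: 84 study days. The requirement is met.

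**What diversion would do.** As an illustration, assume 8, 7 and 6 migraine days in Months 1, 2 and 3, with Month 3 days spread evenly. The sum over Days 1-83 is 8 + 7 + 6 x 27/28 = 20.79. Rescaled by 28/83 it is 7.01, against a Month 3 value of 6. With 8 migraine days in every month, rule 4 returns 8.0 and nothing changes. The distortion comes from rule 4 starting at Day 1; the day numbering only decides who is sent there.

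**The case against.** The strongest reply is that section 6.1 numbers assessments, while section 6.3 sets the diary intervals from the randomization date. On that reading, a programmer numbers diary days by simple subtraction, Days 57-84 are 28 dates ending on the nominal V6 date, and Month 4 absorbs late visits. If the V6 date also counts as blinded, no on-schedule subject is diverted. The reading is sensible and would work, but the SAP does not state it, and it conflicts with section 6.1's placing of the V6 date in the open-label period. The further point that DB study days are undefined, so that Days 0-83 could count as 84, stands in full: the shortfall is one reading and not a certainty.

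A reader might infer more than the documents support.

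- **That more than half of completers are diverted because of the extra subtraction.** If V6 dates are assumed to spread evenly over randomization+79 to +89, then 6 of 11 give fewer than 84 blinded days. That count comes from placing V6 in the open-label period and from the visit window; deleting the minus 1 alone leaves it at 6 of 11. With the V6 date counted as blinded it is still 5 of 11. Nothing in the SAP supports an even spread.
- **That Table 2 puts V6 at randomization+83.** Its Days 7, 28, 56 and 84 for weeks 1, 4, 8 and 12 are 7 times the week, from a Day 0 origin. Only the V2 label differs, so this is a labelling conflict and not a second target date.
- **That the run-in formula distorts baseline.** Table 2 has one scheduled run-in visit, and section 7.4.1 indexes the run-in value from the last diary day. The formula does not feed the endpoint.

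**Conclusion.** The inconsistency is certain: as written, section 6.1 gives two adjacent dates the same study day and does not return Day 84 for a visit 84 days after randomization. Its direct size is small, about 1 day in 28 (3.6%), and the same numbering applies to both arms; no effect on the treatment difference has been shown.

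The larger consequence is conditional. An on-schedule completer falls one day short of 84 only if the V6 date is left in the open-label period and Day 0 is not counted. Both follow from the text of sections 6.1 and 6.3, but the SAP never defines how DB study days are counted. The result assumes V6 exactly at randomization+84. At randomization+85 or later there are at least 84 blinded days on any of these counts. How much diversion would then matter is a property of rule 4, whose Day 1 start is a separate defect.

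The point merits correction because it leaves the primary endpoint's window and its completeness test to a programmer's choice. It does not call for redefining Month 3 or restricting who may fall under the partial-data rule.

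**What to change.** In section 6.1, use study day = date of assessment minus randomization date throughout, and delete the minus 1 from the open-label line. State that the V6 date belongs to the blinded period for the diary count, so that Days 1-84 are the 84 DB study days in sections 6.3 and 7.4.1. This takes nothing from the open-label summaries: section 6.4 starts OL Month 1 at OL Day 1, so OL Day 0 is in no open-label interval. Align Table 2's Day 1 label for V2 with Day 0. As minor tidying, replace the enrollment date with the assessment date in the run-in formula.

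Correct the Day 1 start of the rule 4 sum as a separate point. Completers seen early within the V6 window will still have fewer than 84 study days after this change, so they depend on that correction.

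The cost is SAP wording and one derivation, settled before unblinding. No new data are needed.

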### 6.2 Baseline (Run-in Period)

Generally, a baseline measurement refers to the last non-missing assessment made before the first administration of study treatment (e.g., screening and baseline). For each subject, the run-in period will include the last 28 days of diary data prior to randomization.

### 6.3 Randomized Period

For each subject, the randomized period will be divided into 28-day intervals based on randomization date. An extra interval is included to allow for the visit windows specified in the protocol. These intervals may be used in exploratory analyses.

Month in Randomized Period	Study Days
Month 1	1-28
Month 2	29-56
Month 3	57-84
Month 4	85+

### 6.4 Open-Label Period

For each subject, the open-label period will be divided into 28-day intervals based on number of days in the open-label period, starting with issuance of the open-label period device. The date of issuance of the open-label period device is OL Day 0. An extra interval is included to allow for the visit windows specified in the protocol. These intervals may be used in exploratory analyses.

Month in Open-Label Period	Days in OL Period
OL Month 1	1-28
OL Month 2	29-56
OL Month 3	57 - 84
OL Month 4	85 - 112
OL Month 5	113 - 140
OL Month 6	141 - 168
OL Month 7	169+

OL = Open-label

## **7. SPECIFICATION OF ENDPOINTS AND VARIABLES**

### **7.1 Demographic and Baseline Characteristics**

Sex, age, and race can be used as collected on the eCRF.

### **7.2 Migraine History**

Years since migraine diagnosis will be derived as:

(date of informed consent – date of diagnosis)/365.25

and truncated to 1 decimal point when a full date is available. Otherwise the following partial date rules will be followed:

1. If month and day of diagnosis are missing: The year of diagnosis will be compared to the year in which study informed consent was obtained. If the two years are not the same, then July 1 will be used. If the two years are the same, then January 1 will be used.
2. If day of diagnosis is missing: The year of diagnosis will be compared to the year in which study informed consent was obtained. If the two years are not the same, then 15 will be used for the day. If the two years are the same, then the month of diagnosis will be compared to the month in which study informed consent was obtained. If the months are not the same, then 15 will be used for the day. If the two months are the same, then the first of the month will be used.

Age of onset, number of migraine days in the 4 weeks prior to enrollment, number of headaches (including migraine days) in the 4 weeks prior to enrollment, and number of days per month using acute medications can be used as collected on the eCRF. Whether the migraine is with or without aura will also be used as collected on the eCRF.

### **7.3 Medical and Surgical History**

Medical and surgical history will be collected and coded using the current version of the Medical Dictionary for Regulatory Activities (MedDRA v18.1).

## 7.4 Efficacy

### 7.4.1 Primary Endpoint

The primary endpoint is the change from run-in to the last four weeks (Month 3) of the randomized period in the number of migraine days.

The diary data will collect for each day an indicator (1=Yes, 0=No, or missing) of whether the subject experienced a migraine. One 24 hour period per migraine will be designated as a migraine day.

The visit level value for a given subject is then the sum of the daily diary day indicators of whether the subject experienced a migraine which gives the number of days with a migraine. Calculations are as follows:

$$\text{Run-in Value} = \sum_{i=-z-28}^{-z} \text{Day } i, \text{ where Day } i = 1 \text{ (had a migraine)}$$

where  $z$  represents the subject's last day with diary data during the run-in period.

In the event that a subject does not 28 diary days in the run-in period the following rules will be used to calculate the run-in value:

1. If the number of diary days in the run-in period is less than 21, the run-in value will not be calculated, and will be considered missing.
2. If number of diary days in the run-in period is greater than or equal to 21, but less than 28, the run-in value would be calculated as:

$$\text{Run-in Value} = \sum_{i=-z-x}^{-z} \text{Day } i, \text{ where Day } i = 1 \text{ (had a migraine)}$$

where  $z$  represents the subject's last day with diary data during the run-in period, and  $x$  is the number of days with diary data during the run-in period.

To ensure consistency of the run-in value for all subjects, the value will be adjusted to reflect an estimated number of days with migraine per 28 day interval. For example, if a subject records data for  $x$  days out of 28 days and have  $y$  days with migraine, then the adjusted number of days with migraine in 28 days is  $(28/x)*y$ , with a maximum value of 28.

$$\text{Month 3 Value} = \sum_{i=57}^{84} \text{Day } i, \text{ where Day } i = 1 \text{ (had a migraine)}$$

In the event that a subject does not have at least 84 study days in the DB period the following rules will be used to calculate the Month 3 value:

3. If the number of study days in the DB period is less than 70, the month 3 value will not be calculated, but rather imputed to the run-in value (and thus resulting in a  $\text{Change}_{\text{Run-in}}=0$ , implying no change between periods).

Month 3 Value =Run-in Value

4. If number of study days in the DB period is greater than or equal to 70, but less than 84, the month 3 value would be calculated as:

$$\text{Month 3 Value} = \sum_{i=1}^z \text{Day } i, \text{ where Day } i = 1 \text{ (had a migraine)}$$

where  $z$  represents the subject's last day of participation with diary data present.

To ensure consistency of this value for all subjects, the value will be adjusted to reflect an estimated number of days with migraine per 28 day interval. For example, if a subject records data for  $x$  days out of 28 days and have  $y$  days with migraine, then the adjusted number of days with migraine in 28 days is  $(28/x)*y$ , with a maximum value of 28.

Then the change from Run-in is calculated using the adjusted values as:

$$\text{Change}_{\text{Run-in}} = \text{Month 3 value} - \text{Run-In value}$$

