### 3.5 Sample Size

Table 1 provides the required sample size per treatment group when the number of migraine days per 28-day period is used as the primary outcome measure. Sample size calculations are based on the clinically meaningful difference between active and sham treatment groups in change from baseline. Assuming a type I error of 5% (two-sided) and 90% power, Table 1 displays the required sample sizes for different values of the common standard deviation (2.0, 2.5, 3.0 and 3.5) and the presumed difference between treatment groups (1, 1.5 and 2 days). Selecting an improvement of 1 day and a common standard deviation of 2.5 requires 133 subjects per treatment group. With 15% drop-out during the randomized treatment period, a total of 160 subjects per treatment group (or 320 subjects total) would need to be randomized.

**Table 1: Required Sample Size per Treatment Group  
Assuming Type I Error ( $\alpha$ ) = 5% (two-sided) and 90% Power**

Variability (Common SD*, $\sigma$ )	Clinically Significant Improvement: Active – Sham = $\Delta$		
	1-day	1.5-day	2-day
2.0	86	--	--
2.5	133	60	34
3.0	191	86	49
3.5	259	115	66

\*Estimated standard deviation for change from baseline. Standard deviations for baseline and post treatment scores are between 2.0 to 3.5.

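### The run-in sums in SAP section 7.4.1 cover 29 days for a full diary and x+1 days for a diary of 21 to 27 entries, which does not match the 28-day run-in of section 6.2

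*SAP*

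**What the plan says.** Section 6.2 of the SAP fixes the baseline interval: "the run-in period will include the last 28 days of diary data prior to randomization". Section 6.1 numbers the days: "the day of randomization will be considered study day 0", and the run-in calculation "results in negative numbers".

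Section 7.4.1 then gives two run-in formulas.

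- Full diary: the sum of daily migraine indicators for i from -z-28 to -z.
- Rule 2, for a shorter diary ("If number of diary days in the run-in period is greater than or equal to 21, but less than 28"): the sum for i from -z-x to -z. Here x "is the number of days with diary data during the run-in period". The other symbol, z, "represents the subject's last day with diary data during the run-in period, and" it anchors the window.

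With fewer than 21 diary days the value is missing. Otherwise it is rescaled: for data on x of 28 days with y migraine days, "then the adjusted number of days with migraine in 28 days is" (28/x)*y, capped at 28. The Month 3 value is the sum over days 57 to 84.

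**The concern.** The primary variable is a Month 3 count minus a run-in count, so the two should cover equal lengths of time and the rescaling should divide by the days actually counted. The printed limits fail on both.

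A 29-day baseline set against a 28-day Month 3 shows a small reduction where nothing has changed. A window defined in calendar days but divided by a number of diary entries can leave out recorded days and still divide by them, which lowers the baseline.

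The run-in value enters the primary change, the percentage reduction, the 50% response, Change_OL3 and Change_OL6. Section 7.4.2 carries the method over to headache days and medication days. The value is also a covariate in the ANCOVA, logistic and imputation models. These are the only explicit formulas for it. A programmer who follows them departs from section 6.2; one who silently corrects them departs from section 7.4.1.

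**Working it through.** **1. Number of terms.** An inclusive sum has (upper - lower + 1) terms.

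- Month 3 (7.4.1): 84 - 57 + 1 = 28. This agrees with a four-week period.
- Full-diary run-in: -z - (-z-28) + 1 = 29. Since z cancels, no reading of z gives 28.
- Short-diary run-in: -z - (-z-x) + 1 = x+1, so 22, 25 and 28 days for x = 21, 24 and 27.

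The (28/x)*y step does not remove the 29th term. It is written for x days out of 28, so a full diary has a factor of 28/28 = 1.

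**2. Size for a full diary.** The SAP gives no baseline mean, so 6, 8 and 10 migraine days per 28 are assumed. If a 29th diary entry exists, it adds on average one day's worth of migraine:

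- 6/28 = 0.21 day
- 8/28 = 0.29 day
- 10/28 = 0.36 day

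Each is 1/28 = 3.6% of the baseline. For one subject the change is either 0 or exactly 1 day, and it is 1 day in about 21% to 36% of subjects who have that entry. The response can change as a result: with 4 migraine days in Month 3, a baseline of 7 gives (7-4)/7 = 43%, while a baseline of 8 gives (8-4)/8 = 50%.

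A 29th entry needs a run-in longer than nominal. In Table 2, Visit 1 is Day -28 and Visit 2 has a window of 3 days either side, so this is possible but not the standard case.

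**3. Size for a diary with gaps.** Assume that i indexes calendar days and that x entries lie at random in the 28 days. If the last entry is on the day before randomization, the other x-1 entries lie among 27 days, and the window reaches x of those. The expected number of entries inside the window is 1 + (x-1)*x/27:

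- x = 21: 1 + 20*21/27 = 16.6
- x = 24: 1 + 23*24/27 = 21.4
- x = 26: 1 + 25*26/27 = 25.1
- x = 27: 1 + 26*27/27 = 27

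A simulation that also lets the last entry fall earlier gives the following. The last column applies the share to an assumed true value of 8.

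| x | Entries in window | Share counted | Baseline if truly 8 |
|---|---|---|---|
| 21 | 16.7 | 0.80 | 6.4 |
| 24 | 21.6 | 0.90 | 7.2 |
| 26 | 25.1 | 0.97 | 7.7 |
| 27 | 27.0 | 1.00 | 8.0 |

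The shares are the same at assumed means of 6 and 10. If the x entries are consecutive, the extra calendar day is empty and the error is zero.

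**4. After correction.** Limits of -z-27 to -z give 28 terms. Counting y over all x diary days in the window and multiplying by 28/x returns the true mean (about 6, 8 and 10 in the simulation).

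**The case against.** The strongest reply is that the prose already states the intended rule. Section 6.2 says 28 days, and the rescaling sentence describes x days out of 28 with y migraine days. A careful programmer would probably derive the right value. That bears on how serious the defect is, but it does not make the formulas consistent with the prose.

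A second reply concerns short diaries. If i is meant to index diary days rather than calendar days, a window of x+1 covers all x entries and that error vanishes. This stands as a limit: the SAP does not say which index it means, and the 20% figure also needs random gaps and the lowest permitted x. The full-diary count is 29 under either index.

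Three stronger readings are tempting and are not supported.

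- **A reader might infer that every baseline, and so every change and response, is wrong.** A subject with exactly 28 consecutive entries and none earlier gets the right value. Change_OL3DB and Change_OL6DB subtract the Month 3 value, not the run-in value. A subject imputed under rule 3 has a change from run-in of 0 whatever the baseline.
- **A reader might infer that the treatment comparison is biased, or set 0.36 day against the 1-day design difference of section 3.5.** The error arises before randomization and should fall on both arms alike. A within-arm shift cannot be read against a between-arm difference.
- **A reader might take z as the negative study day of section 6.1.** With z = -1 the limits become Day -27 to Day +1, which would put a post-randomization day into the baseline. The minus sign in front of z suggests that a positive number of days is meant, and section 6.2 places the run-in before randomization. This shows that z needs a definition, not that the plan intends such a sum.

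**Conclusion.** The point holds in this limited form. The printed limits give 29 and x+1 terms, and the first contradicts both section 6.2 and the 28-day Month 3 sum. The definition of the primary baseline is therefore wrong as written.

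The effect is modest and conditional, and the two errors run in opposite directions. Full diaries with an extra entry are inflated by 3.6% on average. Diaries with scattered gaps are understated by about 20% at x = 21, falling to zero at x = 27. The migraine means and the gap pattern are assumptions, and the SAP does not say how often either situation will occur, so no trial-level average can be given.

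What is mainly distorted is the within-arm change from run-in, the percentage reduction, the 50% response, Change_OL3 and Change_OL6, with some added noise in the primary variable. The direction of the primary comparison is not in doubt on this account. The formulas should be fixed before database lock.

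**What to change.** Replace both run-in formulas in section 7.4.1 with one rule.

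1. Take the 28-day run-in window of section 6.2. If it stays in terms of z, use limits -z-27 to -z, define z as the positive number of days before randomization of the last diary entry, and state that i indexes calendar days.
2. Let x be the number of diary days in that window and y the number of migraine days among those same x days.
3. The run-in value is (28/x)*y if x is at least 21, and missing otherwise.
4. Apply the same rule to headache days and acute medication days.

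Keeping the anchor on the last diary entry is preferable to a fixed Day -28 to Day -1 window, which could discard usable earlier entries when a long run-in ends with missing days.

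The cost is a few lines of SAP text and one derivation step, with no new data. Section 4 already requires the SAP to be final before database lock and unblinding, so the correction fits that step.

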## **8. STATISTICAL ANALYSIS**

### **8.1 General Data Handling Rules and Definitions**

If any randomized subject is found to not have valid documented informed consent, that subject's data will be excluded from the report, except as necessary to document the error.

Except where specified all continuous variables will be summarized with descriptive statistics (the number of non-missing values, mean, standard deviation, median, minimum and maximum) and all categorical variables will be summarized with frequency counts and percentages, by treatment group.

Missing data will be maintained as missing unless specified otherwise (see Section 7.4.1 (number of migraine/headache days and associated calculations)). For variables where missing data is imputed, the analysis dataset will include an indication that it is imputed.

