### **8.4 Efficacy Analyses**

#### **8.4.1 Primary Efficacy Analysis**

The primary efficacy analyses will be performed on the ITT population and will be repeated in the PP population, if the sample size between the two groups differ by more than 5%.

Summary statistics for the primary variable, change from 4-week run-in period, will be presented by treatment group. Missing data will be imputed per section 7.4.1.

The number of migraine days will be summarized descriptively for each study phase (run-in and DB) and by treatment group. The summary statistics for each visit, change between the double-blind and 4-week run-in period and percentage change between the double blind and 4-week run-in period (a secondary endpoint) will be summarized by mean, standard deviation, median, minimum, and maximum.

The two-sided, 95% confidence interval (CI) of the difference between the two device groups (active minus sham) in change from 4-week run-in period will be produced and the p-value will be calculated based on a two-sample t-test. If the p-value from the two-sample t-test is less than 0.05, then the null hypothesis will be rejected.

As sensitivity analyses, the two groups will be compared using analysis of covariance (ANCOVA) models with change from 4-week run-in period as the dependent variable and treatment group, and center as fixed effects with the number of migraine days in the 4-week run-in period as a covariate and again with treatment group, center, and aura as fixed effects with number of migraine days in the 4-week run-in period as a covariate. The adjusted means, adjusted mean difference and 95% confidence interval for the adjusted mean difference based on the ANCOVA models will be reported. The p-values tests that the adjusted mean difference between groups at Month 3 equals zero will be reported.

Further sensitivity analyses will investigate the robustness of the analysis to missing data (missing data refers to data points imputed in the calculations presented in section 7.4.1) by implementing multiple imputation and the pattern-mixture model (PMM) with control-based pattern imputation as summarized by Ratitch and O'Kelly (2011). This PMM sensitivity analysis addresses the possibility that the missing data is missing not at random (MNAR), meaning the missing data is not independent of the unobserved outcomes

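### The Month 3 primary value has no minimum number of diary days, and rule 4 for leavers at Days 70-83 sums over the wrong days

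*SAP*

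**What the plan says.** The primary endpoint (SAP 7.4.1) is the change in migraine days from the run-in to Month 3, Days 57-84. The daily diary indicator is coded yes, no or missing.

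- **Run-in.** The test is on diary days: "If the number of diary days in the run-in period is less than 21, the run-in value will not be calculated". From 21 to 27 diary days, the count is scaled to 28 days.
- **Month 3.** The test is on study days: "In the event that a subject does not have at least 84 study days in the DB period the following rules will be used". Rule 3 reads "If the number of study days in the DB period is less than 70, the month 3 value will not be calculated"; the run-in value is used instead, so the change is zero. Rule 4 covers subjects with study days "greater than or equal to 70, but less than 84, the month 3 value would be calculated as" a sum of the daily indicators from Day 1 to z, the last day with diary data.
- **Study day.** Section 6.1 defines it by dates: "Study day = (date of assessment – randomization date".
- **Scaling.** Printed after rule 4: "To ensure consistency of this value for all subjects, the value will be adjusted" to (28/x)*y, where x is the days recorded and y the migraine days, capped at 28. No lower limit on x is given.
- **Flag and sensitivity analyses.** Section 8.1 says: "For variables where missing data is imputed, the analysis dataset will include an indication that it is imputed". Section 8.4.1 defines the scope of multiple imputation (MI) and the pattern-mixture model (PMM): "missing data refers to data points imputed in the calculations presented in section 7.4.1". The complete population analysis (8.4.3.5) keeps subjects whose run-in and double-blind data are neither missing nor imputed.
- **Inherited use.** Section 7.4.2 calculates headache days and acute-medication days like the primary endpoint, and derives response from the Month 3 value.

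**The concern.** The two halves of one change score meet different data standards. The run-in needs 21 diary days. Month 3 needs only that the subject is still in the study on a given date. A subject who reaches Day 84 falls under neither rule 3 nor rule 4, however few Month 3 entries exist, and so enters the primary t-test and the responder analysis on the same footing as a subject with a full diary.

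The ordering is also hard to defend. A subject who leaves at Day 69 with 13 complete Month 3 diary days is set to zero change, while a Day-84 completer with one entry keeps a value which, if scaled, is that entry times 28.

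Rule 4 is a separate error in the same calculation. The endpoint is the last four weeks, but the printed sum starts at Day 1.

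At stake are the precision and traceability of the primary value. Left open, the handling of sparse and empty diaries would be settled during programming.

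**Working it through.** **1. The plan's own figure.** Section 3.5: 1-day difference, SD 2.5, two-sided 5%, 90% power. The noncentral-t calculation gives 133 per group, as stated (power 90.1%). With 160 analysed per group, power is 94.6%. The sample size is not in dispute.

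**2. Precision of a scaled Month 3 value.** Assumptions (not in the SAP): daily migraine rate p = 0.25, that is 7 per 28 days; independent days; gaps at random.
SD = 28 × sqrt(p(1−p)/x):

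| x diary days | 28 | 21 | 14 | 7 |
|---|---|---|---|---|
| SD (days) | 2.29 | 2.65 | 3.24 | 4.58 |

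Under these assumptions the scaled value is unbiased before the cap at 28. The problem is noise.

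**3. Chance of a false 50% response.** No true change, daily rate = run-in/28. Response requires (28/x)·y ≤ run-in/2, so the chance is P(Bin(x, run-in/28) ≤ (run-in/2)·x/28):

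| Run-in value | x=28 | x=7 |
|---|---|---|
| 6 | 12.0% | 18.5% |
| 7 | 5.5% | 13.3% |
| 8 | 6.5% | 36% |

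The range is 5.5-12% with a full diary and 13-36% with seven days. It is uneven because counts are whole numbers.

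**4. Trial level.** If a share f of subjects has x diary days, the variance of the change becomes 6.25 + f × 147 × (1/x − 1/28), where 147 = 28² × 0.25 × 0.75.

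| f | x | SD | Power, 160 per arm | Power, 133 per arm |
|---|---|---|---|---|
| 0 | – | 2.50 | 94.6% | 90.1% |
| 5% | 14 | 2.55 | 93.8% | 89.0% |
| 5% | 7 | 2.65 | 91.9% | 86.5% |
| 10% | 7 | 2.80 | 89.0% | 82.8% |

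**5. Rule 4 as printed.** At p = 0.25 the sum from Day 1 is 0.25 × 70 = 17.5 at z=70 and 0.25 × 83 = 20.75 at z=83. The right answer is 7 per 28 days.
- If x counts the summed days: (28/70) × 17.5 = 7 and (28/83) × 20.75 = 7. The scale is right, but the value averages the whole randomized period.
- If x counts Month 3 days only (14 at z=70, 27 at z=83): (28/14) × 17.5 = 35, capped at 28, and (28/27) × 20.75 = 21.5. The value is grossly inflated.

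Neither is the last-four-weeks value.

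**6. Empty Month 3 diary (x=0).** 28/x cannot be computed. Section 8.1 leaves missing data missing unless 7.4.1 says otherwise, and 7.4.1 has no rule for this subject. The value is therefore missing, with no stated handling in the primary analysis, although section 5.1 uses the ITT set for all primary and secondary efficacy analyses.

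**The case against.** Several points on the other side have force.

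- **Blank days as migraine-free.** A reader might infer that, if scaling is confined to rule 4, a completer's blank days count as zero and bias the count downward. The SAP does not support this: the indicator keeps no and missing apart, and section 8.1 keeps missing data missing. Scaling for all subjects is the more natural reading.
- **An undefined value.** A reader might say that an empty Month 3 diary leaves the endpoint wholly undefined. The section 8.1 default makes it missing, response is defined only for non-missing reductions, and the complete population analysis excludes it. What stands is that the primary analysis has no stated handling. Appendix 1 speaks of imputing missing data generally, but 8.4.1 confines MI and PMM to points imputed under 7.4.1, so cover is unclear.
- **Unflagged values.** A reader might infer that sparse-diary values certainly escape every check. The SAP calls scaled values adjusted and does not say whether they count as imputed. That is an ambiguity, not a proven omission.
- **Study days as days with diary data.** On that reading, 70 of 84 days would guarantee at least 70 − 56 = 14 in Month 3. The date formula in 6.1, and the use of diary days for the run-in only, make it the weaker reading.
- **The per-protocol set.** Its list of major deviations is open-ended, so sparse diaries could be excluded before unblinding. If blank days count as no use, the 67% compliance rule already removes subjects with 18 diary days or fewer (6 × 18 = 108 of 168 stimulations, 64%; 19 days give 114 of 168, 68%). This is a real partial safeguard, but that analysis is not primary and runs only if the sets differ by more than 5%.

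**Conclusion.** The point holds and should be corrected before database lock. Section 7.4.1 sets a diary-day minimum for the run-in and none for Month 3, so completers with sparse diaries receive a primary value of uncontrolled precision. The SD doubles from 2.3 days with a full diary to 4.6 with seven days, assuming a daily rate of 0.25 and independent days. The status of scaled values for the flag, MI, PMM and complete population analyses is not stated. Rule 4 as printed cannot yield the last-four-weeks value on either reading of x.

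The trial-level effect is small: with 160 analysed per arm and 5% of subjects sparse, power goes from 94.6% to 93.8% (x=14) or 91.9% (x=7). It becomes material only if sparse diaries are common or very sparse, and the SAP gives no frequency. A reader might infer that the trial is underpowered, or that setting early leavers to zero change undermines the drop-out allowance in section 3.5. The document does not establish either; the second depends on whether the 1-day difference refers to completers, which the SAP does not say.

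**What to change.** In section 7.4.1:

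1. Define the Month 3 value by the number of diary days within Days 57-84, with a stated minimum. A minimum of 21 matches the run-in. A minimum of 14 keeps leavers at Days 70-83 whose diaries are complete.
2. Apply the 28/x scaling to every subject at or above the minimum, completers included.
3. Correct the rule 4 sum to run from Day 57 to z, with x the diary days in that window.
4. Give subjects below the minimum, including those with no entries, a stated primary value, for example the one in rule 3. Flag them as imputed under section 8.1, and treat them as missing in the MI, PMM and complete population analyses.
5. State whether scaled values count as imputed.
6. Apply the same rules to headache days and acute-medication days.

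Optionally, add Month 1 and Month 2 migraine days to the MI and PMM models. They come from the same diary, and Appendix 1 now names only treatment, center and run-in.

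The cost is SAP wording and programming; no new data are needed. If subjects below the minimum are set to zero change, some zeros are added, which MI and PMM then test. A minimum of 21 would also move leavers at about Days 70-76, who have at most 14-20 Month 3 days, out of rule 4.
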